6.5. Study Drug Compliance

Overall compliance (%) for itacitinib will be calculated for all participants as follows:

$$\text{Overall compliance (relative dose intensity) (\%)} = 100\% \times (\text{total dose administered}) / (\text{intended dose})$$

Intended dose is defined as the sum of the doses prescribed by the investigator accounting both for planned dose reductions as well as those reductions or increases mandated by the investigator.

For IEC infusions, compliance calculations are not applicable. Infusion information collected in eCRF may be listed as needed, including any temporary infusion interruption.

6.6. Prior and Concomitant Medication

Prior medications and concomitant medications will be coded using the WHO Drug Dictionary and summarized by ATC drug class and WHO drug term. Results will be summarized as number and percentage of participants with prior and concomitant medications by ATC class and WHO drug class in the safety population. For the summary of concomitant medication, only medications starting on or after the first dose of study drug will be included. Medications with missing start/end dates will be considered as concomitant medication in the summary. Other medications will be provided in the listing.

7. EFFICACY

A list of planned tables, figures, and listings is provided in [Appendix A](#).

7.1. General Considerations

Unless otherwise specified, for Part 1 of the study, all efficacy analyses will be summarized by treatment group as well as overall using the EAS. For Part 1 of the study, if any of the subgroup includes less than 10% of the overall sample size for that part, the information for this subgroup will only be listed. For Part 2 of the study, all efficacy analyses will be summarized by treatment group using the EAS.

7.2. Analysis of the Primary Efficacy Parameter

7.2.1. Primary Efficacy Analysis

The primary endpoint of the study is CRS rate by Day 14, defined as the percentage of participants experiencing \geq Grade 2 CRS by Day 14 after IEC therapy.

In Part 1, the CRS rate will be calculated for each treatment group as follows:

$$\text{CRS rate} = \frac{x}{n}$$

where n is the number of efficacy evaluable participants, and x is the number of efficacy evaluable participants who experience \geq Grade 2 CRS by Day 14.

The exact 95% CI (2-sided) will be calculated using the Clopper-Pearson method ([Clopper and Pearson 1934](#)), as the following:

$$(B\left(\frac{\alpha}{2}; x, n - x + 1\right), B(1 - \frac{\alpha}{2}; x + 1, n - x))$$

where $B(p; v, w)$ is the p th percentile from a beta distribution with shape parameters v and w , and α is 5%.

In Part 2, the CRS rate and the associated 95% CI will also be calculated for each treatment group, itacitinib 200 mg BID and placebo, in the same way as the analysis for Part 1. The primary efficacy endpoint analysis will be the comparison of the percentage of efficacy evaluable participants experiencing \geq Grade 2 CRS by Day 14 between the 2 treatment groups. The CRS rates will be compared using a 1-sided Z-test at the significance level of 0.05, and a 95% CI (2-sided) for the difference in the CRS rate will be calculated. The following statistical hypothesis will be tested for the primary efficacy endpoint analysis:

$$H_0: \text{CRS}_A \geq \text{CRS}_B \text{ versus } H_1: \text{CRS}_A < \text{CRS}_B$$

where CRS_A and CRS_B will be the CRS rates for itacitinib 200 mg BID and placebo, respectively. The Z-test for the difference between the 2 treatment groups will be based on the following test statistic:

$$z = \frac{\widehat{\text{CRS}}_A - \widehat{\text{CRS}}_B}{\sqrt{\widehat{\text{CRS}}(1 - \widehat{\text{CRS}})\left(\frac{1}{n_1} + \frac{1}{n_2}\right)}}$$

where n_1 and n_2 are the numbers of efficacy evaluable participants for itacitinib 200 mg BID and placebo, respectively, and

$$\begin{aligned}\widehat{CRS}_A &= \frac{x_1}{n_1} \\ \widehat{CRS}_B &= \frac{x_2}{n_2} \\ \widehat{CRS} &= \frac{x_1 + x_2}{n_1 + n_2}\end{aligned}$$

where x_1 and x_2 are the number of efficacy evaluable participants experiencing CRS \geq Grade 2 by Day 14 for the treatment group, itacitinib 200 mg BID and placebo, respectively.

For the 1-sided test specified above, the p-value will be calculated as the probability of $Z \leq z$, where Z is the random variable for the standard normal distribution. If the p-value is smaller than or equal to the significance level at 0.05, the null hypothesis will be rejected. It could be concluded that the \geq Grade 2 CRS rate by Day 14 after Yescarta for itacitinib 200 mg BID is significantly lower than that for placebo.

The 95% CI (2-sided) of the difference in the CRS rate between the 2 treatment groups can be calculated as follows:

$$\widehat{CRS}_A - \widehat{CRS}_B \pm 1.96 * \sqrt{\frac{\widehat{CRS}_A(1-\widehat{CRS}_A)}{n_1} + \frac{\widehat{CRS}_B(1-\widehat{CRS}_B)}{n_2}}.$$

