In Part 2, study treatment is defined as itacitinib 200 mg BID or placebo beginning at Day -3 (pre-IEC) through Day 26 (post-IEC), counting for a total of 30 days of treatment.

See [Figure 1](#) for the study design and [Table 3](#) for the SoA. Adherence to the study design requirements, including those specified in the SoA, is essential and required for study conduct.

Figure 1: Study Design Schema Part 1

Part 1

[figure not shown]

Figure 2: Study Design Schema Part 2

Part 2

[figure not shown]

Table 3: Schedule of Activities

	Screening ^a		Study Treatment								Post-Treatment Follow-Up ^a			Protocol Section
	D -17 to D -4	D -3	D -1	IEC D0	D1	D3	D5	D7	D14 (± 2 d)	D21 (± 2 d)	EOT ^b D28 (± 2 d)	D56 30 d After Last Dose (± 3 d)	D90 (± 1 wk)	EOS D180 (± 2 wk)
Administrative procedures														
Informed consent	X													8.1.1
Contact IRT	X	X									X			8.1.3
Inclusion/exclusion criteria	X	X	X											5.1, 5.2
Demography/medical history	X													8.1.5
Prior/concomitant medications	X	X	X	X	X	X	X	X	X	X	X			6.3
Administer study treatment		X	X	X	X	X	X	X	X	X				6.1
Administer IEC therapy			X											6.2
Document compliance		X	X	X	X	X	X	X	X	X	X			6.1.2
Dispense reminder cards	X	X	X	X	X	X	X	X	X	X	X	X	X	8.1.4
Drug accountability		X	X	X	X	X	X	X	X	X	X			6.1.1
Survival follow-up												X	X	8.9.4
Safety assessments														
Adverse events	X	X	X	X	X	X	X	X	X	X	X	X		8.3.1
ECOG	X		X						X		X			8.3.4
Physical examination	X		X								X			8.3.2
Vital signs	X	X	X	X	X	X	X	X	X	X	X	X		8.3.3
ECHO	X													8.9.3
12-lead ECG	X													8.9.3
Disease assessments														
FDG-PET CT/MRI ^c	X										X		X	8.4
Bone marrow evaluation	X													8.4
Endpoint assessments														
Temperature monitoring		X	X	X	X	X	X	X	X	X	X			8.3.3
CRS assessment (ASBMT CRS consensus grading) ^d											X			8.2.1
ICANS assessment (ASBMT ICE consensus grading) ^e											X			8.2.2
Lee's CRS revised grading system			X	X	X	X	X	X	X	X	X	X	X	8.2.3

Table 3: Schedule of Activities (Continued)

	Screening ^a	Study Treatment										Post-Treatment Follow-Up ^a			Protocol Section
		D -17 to D -4	D -3	D -1	IEC D0	D1	D3	D5	D7	D14 (± 2 d)	D21 (± 2 d)	EOT ^b D28 (± 2 d)	D56 30 d After Last Dose (± 3 d)	D90 (± 1 wk)	EOS D180 (± 2 wk)
Local laboratory assessments^f															
Hematology	X	X		X	X	X	X	X	X	X	X	X	X	8.3.5	
Serum chemistries (including LDH)	X	X		X	X	X	X	X	X	X	X			8.3.5	
Coagulation panel	X	X				X					X			8.3.5	
Lipid panel	X										X			8.3.5	

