Hepatitis screening	X													8.3.5.2	
Pregnancy testing	X	X									X	X		8.3.5.1	
Lumbar puncture with paired blood samples ^g	Only if performed based on SOC													—	
Urinalysis	X										X			8.3.5	
CRP	X	X		X	X	X	X	X	X	X	X			8.3.5	
Ferritin levels	X	X		X	X	X	X	X	X	X	X			8.3.5	

ASBMT = Association for Blood and Bone Marrow Transplantation; CRP = C-reactive protein; CRS = cytokine release syndrome; CT = computed tomography;

ECG = electrocardiogram; ECHO = echocardiogram; ECOG = Eastern Cooperative Oncology Group; EOS = end of study; EOT = end of treatment;

FDG-PET = fluorodeoxyglucose positron emission tomography; ICANS = immune effector cell-associated neurotoxicity syndrome; ICE = immune effector cell-associated encephalopathy; IEC = immune effector cell; LDH = lactate dehydrogenase; MRI = magnetic resonance imaging; PBMC = peripheral blood mononuclear cell; PK = pharmacokinetics; SOC = standard of care.

^a Decentralized assessments are acceptable during screening and post-treatment (see Section 11.1).

^b EOT: Treatment will end on Day 26; however, the participant will be assessed at Day 28 ± 2 days. If a participant ends treatment early, an EOT visit should be conducted at the time that the participant discontinues treatment.

^c If hematologic disease assessments are performed at different timepoints, based on institutional guidelines, then this is acceptable. All disease assessments should be captured in the eCRF.

^d CRS will be evaluated at each visit during the study. In addition, participants should be monitored during the study and evaluated for CRS if fever is present.

^e ICANS will be evaluated at each visit during the study. In addition, participants should be monitored during the study and evaluated for ICANS if there are signs and symptoms relating to neurotoxicity.

^f Screening for central laboratory assessments must be performed within 7 days of Day -3. If screening laboratory assessments are performed within 3 days before Day -3, then the tests do not need to be repeated on Day -3. Any laboratory samples collected on Day -3 must be collected before study treatment administration.

^g Lumbar puncture is not required; however, if one is performed per SOC, then it should be captured in the eCRF.

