- The dose of itacitinib 200 mg BID was selected for the Part 2 expansion, based on nonclinical experiments and using a population PK model. Nonclinical experiments utilizing a dose which achieved a similar level of target coverage as itacitinib 200 mg QD in humans, demonstrated that itacitinib does not impact CAR-T function. However, in vitro experiments showed that T-cell proliferation may be impacted at high concentrations with continuous exposure (ie, > 500 nM; see [Figure 4](#)) which exceed those following 200 mg QD after protein binding adjustment. Using a population PK model (DMB-20.40), the concentration-time profiles following 200 mg BID were simulated. Free concentrations are predicted to remain below 500 nM in at least 95% of participants, while the target coverage is maintained for a vast majority of the BID dosing interval as compared to less than half of the QD dosing interval (see [Figure 3](#)).

Figure 3: Simulated Free Itacitinib Concentration-Time Profiles

Blue = 400 mg, Green = 200 mg, Black = 100 mg. Solid = QD, Dashed = BID. Dotted red = 500 nM, Dotted purple = 49 nM. Free concentrations are used to account for in vivo protein binding which was not present in the in vitro T-cell proliferation experiments. The IC50 is also protein binding adjusted as it was calculated using total plasma concentrations (141nM for total concentrations).

Part 2 is a randomized, placebo-controlled portion of the study to determine the efficacy and safety of itacitinib 200 mg BID. Investigators and participants will be blinded. Approximately 46 participants treated with Yescarta for relapsed or refractory large B-cell lymphoma or follicular lymphoma will be enrolled in Part 2 of the study. Participants will be randomized in a 1:1 ratio to receive either itacitinib or placebo. The comparison to placebo is relevant to provide a well-controlled assessment of efficacy, and it is justified considering that there is no available drug therapy to be used as a comparator.

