6.3. Measures to Minimize Bias: Randomization and Blinding

In Part 2, participants will be randomized to receive either itacitinib 200 mg BID or placebo. Investigators and participants will be blinded.

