10. STATISTICS

10.1. Sample Size Determination

Part 1 is a single-arm open-label study. The sample size calculation is based on the primary endpoint of \geq Grade 2 CRS rate by Day 14. It was considered that $60\% \geq$ Grade 2 CRS by Day 14 is clinically relevant in this setting. Based on a target rate of 60%, a sample size of 62 will provide 90% power to exclude a higher limit of 79% of a 2-sided 95% CI. The sample size calculation is based on an efficacy evaluable analysis set (see Section [10.2](#) for definition).

[Table 18](#) represents CRS Rates and CIs for a sample size of 62.

Table 18: CRS Rates and 95% Confidence Intervals

Sample Size	Number of CRS	CRS Rate (%)	95% Confidence Interval (%)
62	36	58.1	44.8, 70.5
62	38	61.3	48.1, 73.4
62	40	64.5	51.3, 76.3
62	42	67.7	54.7, 79.1
62	44	71.0	58.1, 81.8

Part 2 is a randomized expansion of the study; itacitinib 200 mg BID versus placebo.

As in Part 1, the primary endpoint is Grade \geq 2 CRS rate by Day 14. Assuming Grade \geq 2 CRS rate in the placebo arm is 50% ([Nastoupil et al 2020](#)) and a 20% in the treatment arm (~30% change in CRS rate), a sample size of 23 evaluable participants per group would provide 70% power based on a 1-sided Type-I error rate of 5%. Sufficient number of participants will be enrolled to yield 23 evaluable participants in each group.

A Bayesian interpretation for the selection and impact of the sample size can be provided in terms posterior probabilities. As the response rate based on CRS grade has a binomial (n, p) distribution with s number of responders out of n participants, it is common to use a conjugate Beta (a, b) prior which will lead to a Beta(a + s, b + n - s) posterior distribution. For this exercise, we will assume a noninformative Beta(1,1) (~ Uniform(0,1) prior).

[Table 19](#) presents scenarios of Bayesian posterior probability of demonstrating a treatment difference ($\geq 30\%$) by Day 14 in response rates, between the itacitinib 200 mg BID group and the placebo group, under various response rates (number and percentage of responders).

Table 19: Bayesian Posterior Probability of Demonstrating a Treatment Difference

N ^a (%) 200 BID Group	N ^b (%) Placebo	Posterior Probability ^c
2 (8.7)	9 (39.1)	43.7
	12 (52.5)	79.4
	14 (60.9)	93.4
5 (21.7)	9 (39.1)	13.9
	12 (52.5)	45.9
	14 (60.9)	67.9
7 (30.4)	9 (39.1)	4.7
	12 (52.5)	22.7
	14 (60.9)	44.7

^a Number of participants with CRS \geq Grade 2, out of 23 participants, in the 200 mg BID group.

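### The Part 2 primary Z-test is valid, but it uses none of the baseline ferritin, CRP or LDH already collected; adjusting for one named in advance may add 0 to 10 points of power and guards against chance imbalance

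*SAP*

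**What the plan says.** The Part 2 primary comparison in SAP 7.2.1 is a pooled-variance test of two proportions: "The CRS rates will be compared using a 1-sided Z-test at the significance level of 0.05". Its statistic contains only the event counts and arm sizes. SAP 3.3 calls the same comparison a two-sample t test, and Protocol 10.4.1.2 asks only for a one-sided test. None of the three names a covariate or a stratum. Protocol 10.4.2.1 mentions Cochran-Mantel-Haenszel tests among the secondary comparisons, but the readable text gives no strata.

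Protocol 10.1 assumes that the "CRS rate in the placebo arm is 50" percent and the itacitinib rate 20%, and concludes that "a sample size of 23 evaluable participants per group would provide 70% power based on a 1-sided Type-I error rate of 5" percent.

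On allocation, Protocol 2.3.4 says "Participants will be randomized in a 1:1 ratio to receive either itacitinib or placebo". Protocol 6.3 adds only "In Part 2, participants will be randomized to receive either itacitinib 200 mg BID or placebo". No stratification factor is stated there or in SAP 3.2.

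The Schedule of Activities (Protocol Table 3) has rows for "Ferritin levels", CRP and serum chemistries with LDH, each at screening and Day -3. Its laboratory footnote requires Day -3 samples to precede study treatment. It also waives the Day -3 repeat when screening tests fall within the 3 days before.

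**The concern.** With 46 participants and 70% power, Part 2 has little information to spare. A pre-treatment variable that predicts Grade 2 or higher CRS would reduce the residual variance of the treatment comparison without adding a patient or a sample. The trial already collects three candidates, and the primary analysis ignores them.

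The second issue is chance imbalance. At 23 per arm, sizeable baseline differences are common. If a prognostic marker is unbalanced, the unadjusted result will be questioned, and the SAP has no prespecified analysis of the primary endpoint to answer with. The sensitivity analysis in SAP 7.2.1.2 deals only with early dropouts. The supportive analyses in 7.2.1.3 compare across study parts. The Bayesian analysis in Protocol 10.4.1.2 rests on the same unadjusted counts.

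**Working it through.** **Inputs.** 23 per arm, rates 50% and 20%, one-sided alpha 0.05 (Protocol 10.1); pooled Z-test (SAP 7.2.1); 1:1 allocation (Protocol 2.3.4). Prognostic strength is not in the documents and is varied as an assumption.

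**Step 1: the plan's own figure.** Pooled rate = (0.50 + 0.20)/2 = 0.35.

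- SE under the null = sqrt(2 × 0.35 × 0.65 / 23) = 0.1407
- SE under the alternative = sqrt((0.50 × 0.50 + 0.20 × 0.80) / 23) = 0.1335
- Power = Phi[(0.30 − 1.645 × 0.1407) / 0.1335] = Phi(0.514) = 69.6%

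Exact binomial enumeration of the SAP test gives 69.2%. Its exact size is 4.7% to 5.5% for common rates from 10% to 60%. The 70% claim is sound. For scale, 80% power without adjustment needs 31 per arm.

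**Step 2: approximate gain.** If a covariate explains a share R2 of outcome variance, multiply both variances by (1 − R2). At R2 = 0.10 the SEs become 0.1334 and 0.1267, and power = Phi[(0.30 − 1.645 × 0.1334) / 0.1267] = 73.7%. This equals an effective size of 23/0.90 = 25.6 per arm. Other values: R2 0.02 gives 70.4%, 0.05 gives 71.6%, 0.20 gives 78.2%, 0.25 gives 80.6%.

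**Step 3: simulation of the actual method.** One standard normal covariate; logistic outcome with marginal rates held at 50% and 20%; linear model on treatment and covariate; one-sided model-based t-test on 46 − 3 = 43 df; 40,000 trials per setting. Monte Carlo 95% error is 1.96 × sqrt(0.7 × 0.3 / 40,000), about 0.45 points.

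| Assumed odds ratio per SD | R2, placebo arm | Z-test power | Adjusted power | Gain (points) |
|---|---|---|---|---|
| 1 | 0% | 69.5% | 69.5% | 0.0 |
| 1.5 | 4% | 69.0% | 70.3% | 1.3 |
| 2 | 10% | 69.3% | 73.0% | 3.7 |
| 3 | 20% | 69.0% | 76.1% | 7.1 |
| 4 | 27% | 69.3% | 79.1% | 9.8 |

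The gains are a little below Step 2 because the same marker explains less variance in the arm with fewer events. A separate run indexed by placebo-arm AUC agrees: 0.63 gives 71.1%, 0.69 gives 73.3%, 0.74 gives 76.1%, 0.81 gives 80.3%.

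**Step 4: error rate by method.** With one covariate and null rates of 35% and 50%:

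- Linear model, model-based t-test: 4.7% to 5.4%
- Logistic likelihood-ratio test: 5.4% to 6.1%
- Standardised risk difference, uncorrected: 5.3% to 5.9%

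HC3 robust errors cost power instead: 68.1% against 69.5% unadjusted for a useless covariate, and 68.5% against 69.3% at odds ratio 1.5. Three useless covariates lower the linear model to 67.9%.

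**Step 5: chance imbalance.** The between-arm difference in covariate means has SD sqrt(2/23) = 0.295. A difference above 0.3 SD in either direction occurs in 31% of trials, and above 0.5 SD in 9%. At odds ratio 2, given a difference above 0.3 SD:

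- against itacitinib: Z-test power 51.5%, adjusted 70.6%
- favouring itacitinib: Z-test false-positive rate about 10%, adjusted about 5%

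**The case against.** The strongest reply is that nothing is broken. The Z-test is valid, matches the sample-size calculation and delivers its stated power. Its type I error already averages over chance imbalance, so Step 5 describes conditional behaviour, not a flaw. All of that stands.

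The gain is also hypothetical. Neither document says how well ferritin, CRP or LDH predicts Grade 2 or higher CRS. The assays are run at local laboratories (Protocol 8.3.5), which may weaken any relation. This stands too, and is why the gain is given as a range from zero.

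A reader might expect Part 1 to supply the best marker. It is unlikely to do so reliably. Protocol 2.3.3 reports 3 of 26 participants with Grade 2 CRS and none higher. At that rate 62 participants yield about 7 events (62 × 3/26 = 7.2), all on itacitinib and spread over several cell products, whereas Part 2 is Yescarta only. In a simulation with three independent markers, one truly prognostic, Part 1 data picked the right one 48% of the time at odds ratio 1.5 and 67% at 2.0.

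Changing a primary test also carries a credibility cost here. The design text following Protocol Table 7 says the sponsor is unblinded in Part 2. This objection stands and shapes the fix.

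A worry about few events (23 × 0.50 + 23 × 0.20, about 16) fits multi-parameter logistic models better than one covariate in a linear model, which held its size in Step 4.

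**Conclusion.** This is a missed efficiency, not an error. One baseline covariate may add about 0 to 10 points to the 70% power: about 1 if weakly prognostic, 3 to 7 if moderate, 10 if strong. The range rests on assumed prognostic strength and on one roughly normal covariate. Type I error stays near 5% with the model-based linear analysis. If the covariate is useless, power is essentially unchanged.

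Three stronger readings are tempting and are not supported:

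- That the plan certainly gives up power: this would need a known prognostic strength, which the documents do not give.
- That adjustment is free under any method: HC3 loses power for weak markers, and the likelihood-ratio and uncorrected standardised analyses run above 5%.
- That randomization is unstratified: the documents state no factor, but the Part 2 schema is not shown and IRT details are left to a manual (Protocol 8.1.3).

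**What to change.** In SAP 7.2.1, for Part 2:

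1. Estimate the risk difference from a linear model with treatment and one covariate named now, for example log ferritin. Do not select it by searching Part 1 data.
2. Define the covariate as the last nonmissing value before the first dose of study drug. SAP 4.1.5 allows a pre-IEC baseline for efficacy, which could fall after dosing has begun. A definition tied strictly to Day -3 would lose participants whose screening tests were not repeated.
3. State a simple missing-value rule, such as the overall median across both arms.
4. Use the model-based one-sided t-test at 0.05, not HC3, likelihood-ratio or uncorrected standardisation. Keep the unadjusted Z-test as a sensitivity analysis.
5. Document that the choice was made without reference to Part 2 outcomes by arm. If that cannot be shown, keep the Z-test as primary and make the adjusted model the prespecified supportive analysis.

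The same edit should reconcile the test named in SAP 3.3 with 7.2.1. The cost is SAP wording and slightly more analysis work; no patients, visits or assays are added.

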7.2.1.1. Handling of Missing Data in Primary Analysis

For the primary analysis, if a participant drops out of the study prior to reaching Day 14 after IEC without experiencing a CRS event of \geq Grade 2, the participant will be considered as not experiencing \geq Grade 2 CRS by Day 14. See Section 7.2.1.2 for the sensitivity analysis that is planned in this regard.

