As of the preplanned interim analysis data cutoff (08 JAN 2021), 26 participants were enrolled, 25 participants had completed Day 28 (EOT visit), and 26 participants had completed Day 14. The primary intent of this analysis was to minimize unnecessary exposure to itacitinib in the event of futility of preventing CRS. Of the 26 participants, 3 (11.5%) participants experienced CRS Grade 2, and there was no participant with \geq Grade 3 CRS. Two participants received tocilizumab for CRS Grade 1. Five (19.2%) participants had \geq Grade 2 ICANS. Results from this interim analysis have shown itacitinib to be well-tolerated, with preliminary evidence of clinical activity for the prevention of CRS and ICANS.

A PK analysis was also performed, based on the interim data cutoff described above. Exposures were generally similar in this patient population to those observed in other patient populations receiving the same dose at steady state, 200 mg QD. The exposure range for itacitinib when dosed with axicabtagen ciloleucel or tisagenlecleucel are highly overlapping, although limited patients had received tisagenlecleucel. At the time of this interim analysis there was no apparent

[figure not shown]
exposure/response relationship between measures of exposure (ie, AUC, C_{max} , and C_{min}) and CRS or ICANS grade.

2.3.4. Rationale for Part 2

An additional dosing regimen of itacitinib will be explored in an expanded, Part 2, of the study based on the following rationale:

- Although preliminary data from Part 1 are promising, target coverage following 200 mg QD is < 10 hours, suggesting BID dosing may offer greater target coverage over 24 hours.

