3.4. Sample Size Considerations

Part 1 is a single-arm open-label study. The sample size calculation is based on the primary endpoint of \geq Grade 2 CRS rate by Day 14. It was considered that $60\% \geq$ Grade 2 CRS by Day 14 is clinically relevant in this setting. Based on a target rate of 60%, a sample size of 62 will provide 90% power to exclude a higher limit of 79% of a 2-sided 95% CI. The sample size calculation is based on an EAS (see Section [5.3](#) for definition).

[Table 2](#) represents CRS rates and CIs for a sample size of 62.

Table 2: Cytokine Release Syndrome Rates and 95% Confidence Intervals

Sample Size	Number of CRS	CRS Rate (%)	95% CI (%)
62	36	58.1	44.8, 70.5
62	38	61.3	48.1, 73.4
62	40	64.5	51.3, 76.3
62	42	67.7	54.7, 79.1
62	44	71.0	58.1, 81.8

Part 2 is a randomized expansion of the study; itacitinib 200 mg BID versus placebo.

As in Part 1, the primary endpoint is Grade \geq 2 CRS rate by Day 14. Assuming Grade \geq 2 CRS rate in the placebo arm is 50% ([Nastoupil et al 2020](#)) and is 20% in the treatment arm (~30%

change in CRS rate), a sample size of 23 evaluable participants per group would provide 70% power based on a 1-sided Type I error rate of 5%. Sufficient number of participants will be enrolled to yield 23 evaluable participants in each group.

A Bayesian interpretation for the selection and impact of the sample size can be provided in terms posterior probabilities. As the response rate based on CRS rate has a binomial (n, p) distribution with s number of responders out of n participants, it is common to use a conjugate Beta (a, b) prior which leads to a Beta($a + s$, $b + n - s$) posterior distribution. For this exercise, we assume a noninformative Beta(1,1) (\sim Uniform(0,1) prior).

Table 3 presents scenarios of Bayesian posterior probability of demonstrating a treatment difference ($\geq 30\%$) by Day 14 in CRS rates, between the itacitinib 200 mg BID group and the placebo group, under various CRS rates assumption (number and percentage of participants experiencing \geq Grade 2 CRS).

Table 3: Bayesian Posterior Probability of Demonstrating a Treatment Difference

N^a (%) 200 BID Group	N^b (%) Placebo	Posterior Probability^c
2 (8.7)	9 (39.1)	43.7
	12 (52.5)	79.4
	14 (60.9)	93.4
5 (21.7)	9 (39.1)	13.9
	12 (52.5)	45.9
	14 (60.9)	67.9
7 (30.4)	9 (39.1)	4.7
	12 (52.5)	22.7
	14 (60.9)	44.7

^a Number of participants with CRS \geq Grade 2, out of 23 participants, in the 200 mg BID group.

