7.2.1.2. Sensitivity Analysis

A sensitivity analysis will be performed on the primary efficacy endpoint. For this analysis, participants who dropped out of the study prior to reaching Day 14 after IEC without experiencing any CRS event of \geq Grade 2 will be excluded. If there is no participant in this situation, the sensitivity analysis will not be performed. The same method for the primary efficacy endpoint analysis specified in Section 7.2.1 will be used for this analysis, except that no hypothesis testing will be conducted here.

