7.3.4. Cytokine Release Syndrome-Free Survival

The CRS-free survival analysis will be performed using the Kaplan-Meier method, with the following events considered as the events of interest:

- CRS of \geq Grade 2
- Death
- Initiation of tocilizumab with the indication of CRS treatment
- Initiation of corticosteroids with the indication of CRS treatment

For participants who experience any of the events of interest mentioned above, the time-to-event variable will be calculated as the number of days from IEC therapy to the first occurrence of the events of interest. For participants who do not experience any of the events of interest, they will be treated as censored observations, and the time-to-event variable will be calculated as the number of days from Day 0 to the date of the last available CRS assessment by Day 28. The numbers of participants who do and do not experience any of the events of interest will be summarized. The median CRS-free survival in days, and the CRS-free survival rates on Days 7, 14, 21, and 28 will be included in the summary.

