1.5 Others		
1.5.1	Summary of General Medical History	Safety
1.5.2	Summary of Death	
2 Efficacy (add subgroup analysis as needed)		
2.1.1	Summary of CRS Rate by Day 14 After IEC Therapy	EAS
2.1.1.1	Sensitivity Analysis: Summary of CRS Rate by Day 14 After IEC Therapy – Excluding Participants Who Drop Out of the Study Prior to Day 14 Without Experiencing \geq Grade 2 CRS	EAS
2.2.1	Summary of ICANS Rate by Day 28 After IEC Therapy	EAS
2.2.2.1	Summary of Onset and Duration of ICANS by Day 28 After IEC Therapy	EAS
2.2.2.2	Summary of Onset and Duration of ICANS During the Lifetime of the Study	EAS
2.2.3.1	Summary of Onset and Duration of CRS by Day 28 After IEC Therapy	EAS
2.2.3.2	Summary of Onset and Duration of CRS During the Lifetime of the Study	EAS
2.2.4.1	Summary of CRS-Free Survival by Day 28 After IEC Therapy	EAS
2.2.4.2	Summary of CRS Rate Within 48 Hours and by Day 28 After IEC Therapy	EAS
2.2.4.3	Summary of Tocilizumab and Corticosteroid Use for CRS Treatment	EAS
[REDACTED]	[REDACTED]	[REDACTED]
[REDACTED]	[REDACTED]	[REDACTED]

Table No.	Title	Population
[REDACTED]	[REDACTED]	[REDACTED]
[REDACTED]	[REDACTED]	E [REDACTED]
[REDACTED]	[REDACTED]	[REDACTED]
[REDACTED]	[REDACTED]	[REDACTED]
Safety		

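### Does scoring early dropouts as CRS-free, checked only by leaving them out, make the Part 2 primary result unsafe?

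*SAP*

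**What the plan says.** The Part 2 primary analysis (SAP 7.2.1) is a one-sided pooled Z-test at 0.05 on the proportion with Grade 2 or higher CRS by Day 14. The counts in the numerators "are the number of efficacy evaluable participants experiencing CRS" of that grade, over all efficacy evaluable participants. A participant who was infused and then left therefore stays in the denominator.

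For someone who leaves before Day 14 without such an event, SAP 7.2.1.1 states that "the participant will be considered as not experiencing" it. SAP 7.2.1.2 then repeats the analysis without "participants who dropped out of the study prior to reaching Day 14 after IEC without experiencing any CRS event of" Grade 2 or higher, using the same method "except that no hypothesis testing will be conducted here". If there are no such participants, it is not run. Appendix A lists the output as Table 2.1.1.1, with a title ending in "Excluding Participants Who Drop Out of the Study Prior to Day 14 Without Experiencing" Grade 2 or higher CRS.

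SAP 7.3.4 treats the same people in another way. In the Kaplan-Meier analysis of CRS-free survival, death is an event. Of participants with none of the listed events it says that "they will be treated as censored observations", with follow-up ending at the last CRS assessment. Day 14 rates are reported. Neither 7.2.1.1 nor 7.2.1.2 mentions death.

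**The concern.** Scoring dropouts as non-events lowers the observed CRS rate in whichever arm loses more people. If that is the itacitinib arm, the rule favours the drug. The designated check removes dropouts, which amounts to assuming that they had the same risk as those who stayed. Neither analysis of the primary endpoint allows dropouts to have done worse than completers, which is what a sceptical reader will ask about. With 23 per arm, one or two reclassified participants can carry the p-value across 0.05.

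The silence on early death adds to this. A death before Day 14 without Grade 2 or higher CRS is a non-event by construction, and it is not stated whether such a person has dropped out for the purpose of the exclusion table. At stake would be a claim of CRS prevention resting on outcomes that were never observed.

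**Working it through.** **Inputs.** 23 evaluable per arm, 50% versus 20%, one-sided 0.05, stated power 70% (Protocol 10.1, SAP 3.4). Test and interval from SAP 7.2.1. Neither document gives a Part 2 dropout rate, so every dropout count below is an assumption.

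**The plan's own figure.** Power = Φ[(0.30 − 1.645·√(2·0.35·0.65/23)) / √((0.25+0.16)/23)] = Φ[(0.3000 − 0.2314)/0.1335] = Φ(0.514) = 69.6%. Exact enumeration of the Z-test gives 69.2%. The stated 70% reproduces.

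**How many dropouts are plausible.** Protocol 2.3.3 reports 26 enrolled at the Part 1 interim and that "26 participants had completed Day 14". The exact 95% upper limit for 0 of 26 is 1 − 0.025^(1/26) = 13.2%, and 0.132 × 23 is about 3 participants.

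**One example, 5/23 versus 12/23, with two itacitinib dropouts.**
- As planned: difference −0.3043, pooled rate 17/46, standard error 0.1423, z = −2.138, p = 0.016.
- One recounted as an event (6/23): p = 0.035.
- Both recounted (7/23): difference −0.2174, pooled rate 19/46, standard error 0.1452, z = −1.497, p = 0.067.
- Both excluded (5/21 versus 12/23): −0.2836 ± 1.96 × 0.1396, or −0.557 to −0.010. Zero is still excluded.

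**The six scenarios in SAP Table 3 that are significant under the Z-test.**

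| Events, itacitinib v placebo | p as planned | Itacitinib dropouts as events needed for p > 0.05 |
|---|---|---|
| 2 v 9 | 0.008 | 2 (p = 0.051) |
| 5 v 12 | 0.016 | 2 (p = 0.067) |
| 7 v 14 | 0.019 | 2 (p = 0.070) |
| 5 v 14 | 0.0035 | 4 |
| 2 v 12 | 0.0007 | 5 |
| 2 v 14 | 0.0001 | 7 |

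With two excluded, the upper limits for the first three are −0.060, −0.010 and +0.008.

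**False-positive rate.** Both true rates 50%, all dropouts before any event, exact enumeration:

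| Dropouts | Itacitinib only | Equal in both arms |
|---|---|---|
| 0 | 5.2% | 5.2% |
| 1 | 6.8% | 4.8% |
| 2 | 8.7% | 4.4% |
| 3 | 11.1% | 4.1% |

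Dropout on placebo only lowers power at 20% versus 50% from 69.2% to 63.9%, 58.1% and 52.1%. Only a one-sided imbalance favours the drug.

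**How often it would matter.** Take 20% versus 50% with exactly two itacitinib dropouts before any event and none on placebo. The result is significant with probability 0.743. If both dropouts are taken to be events, 35% of those results are lost, and the exclusion interval still excludes zero in 43% of the lost ones. That is a worst case: two events out of two have probability 0.2² = 4% at a 20% risk and 0.5² = 25% at 50%. Weighting each significant table by the binomial chance of 0, 1 or 2 unseen events gives:

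| Risk among dropouts | Significant results that would reverse | Reversed while the exclusion interval still excludes zero |
|---|---|---|
| 20% | 6.8% | 0.6% |
| 50% | 17.2% | 3.8% |

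The same enumeration with three itacitinib-only dropouts gives 1.4% and 7.9% in the last column.

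**The case for a change.** The case for adding something is respectable. Part 1 used once-daily dosing and Part 2 uses twice-daily, so its retention record transfers imperfectly, and 0 of 26 still allows about 3 of 23. In two of the three Table 3 scenarios that tip at two dropouts, the planned exclusion interval would not show it. Part of the interval's apparent sensitivity is only that a two-sided 95% interval is stricter than a one-sided 5% test. CRS-free survival is no full substitute: it is a composite that includes treatment for CRS, no between-arm test is stated, and it is not labelled as a sensitivity analysis of the primary endpoint. A count fixed before unblinding carries more weight than one produced later.

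All of that stands, but none of it shows a planned result to be wrong. A tipping count would leave the rule, the test and the exclusion analysis as they are. It also leaves the analyst nothing to choose. Table 2.1.1 gives events and denominators by arm, Table 2.1.1.1 gives the denominators after exclusion, and their difference is the number of dropouts per arm. The Z-test can then be recomputed by hand, as above. Appendix A already lets the table list be modified without an SAP amendment where the nature of the analysis is unaffected.

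On early death, the numerator in SAP 7.2.1 already settles the primary score. What remains open is whether a death counts as leaving the study in the exclusion table. A footnote settles that, and deaths, fatal adverse events and withdrawals with reasons are tabulated anyway. Counting deaths as events within 7.2.1.2 would blur an exclusion analysis with a composite that 7.3.4 already supplies.

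**Conclusion.** No change follows. The rule is stated in advance and varied once by design, and the same participants are handled differently again in CRS-free survival. Harm requires four things together: dropout from the study (not merely from study drug), concentrated on itacitinib, with unseen Grade 2 or higher CRS, in a result near the boundary. Several features make the first two unlikely. Assessments continue after treatment stops (Protocol Table 2 and 8.8), people never infused are outside the efficacy set (SAP 5.3), participants and investigators are blinded (Protocol 6.3), and none of 26 was lost by Day 14 in Part 1.

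If exactly two such dropouts did occur, a reversal missed by the exclusion interval would affect about 0.6% of significant results at a 20% dropout risk and 3.8% at 50%. These figures rest on assumed dropout counts, none of them on placebo, and on the design rates of 20% and 50%. They would be larger with three or more one-sided losses. In that event the report's own tables would show the imbalance and allow the tipping count to be given alongside them. The missing sentence on early death is a detail that analysts can settle with a footnote.
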